Appendix 2 Management and Discontinuation Criteria for Abnormal Liver Chemistry Tests

Management and Discontinuation Criteria for Abnormal Liver Chemistry Tests have been designed to ensure patient safety and evaluate liver event etiology. (See Guidance for Industry Drug-Induced Liver Injury: Premarketing Clinical Evaluation, FDA: July 2009)

1. Abnormal Liver Chemistry Criteria

The investigator or qualified designee must review patient laboratory test results to identify if any levels meet the following criteria:

- a. AST or ALT >5 \times ULN
- b. AST or ALT >3 × ULN and total bilirubin >2 × ULN or, if measured, PT or INR >1.5 (Note: The specified INR threshold does not apply to patients receiving anticoagulant therapy.)
- c. AST or ALT >3 × ULN with signs or symptoms consistent with hepatitis or hypersensitivity (eg, fatigue, nausea, vomiting, right upper quadrant pain or tenderness, jaundice, fever, rash, eosinophilia of >5%)

2. Action to be Taken by Investigator

If any abnormal liver chemistry criterion is met, the investigator or qualified designee must do the following:

- Report this event to the sponsor as soon as possible, but no later than 72 hours after learning of its occurrence by completing the appropriate eCRF page. If the EDC system is unavailable or technical difficulties are encountered, the event must be reported by completing the paper Liver Event Form and sending it by fax or e-mail to the sponsor. Local fax numbers and the e-mail address are provided in the table in Section 7.6.5.7.2. A sample of the paper Liver Event Form and further instructions are included in the site regulatory binder.
- Patients must be instructed to discontinue study medication if any one of the criteria in Appendix 2, Section 4 ("Drug Discontinuation Criteria Due to Abnormal Liver Chemistry Tests") is met. Study drug may also be discontinued based on the clinical judgment of the investigator. The investigator or qualified designee should not re-challenge the patient with the investigational product.
- Following the initial observed elevation, every effort should be made to have the patient return to the clinic within 72 hours to repeat liver chemistry tests and for further hepatic evaluation.
- Every effort should be made to have the patients monitored 2 to 3 times per week until abnormal liver chemistry tests (ALT, AST, ALP, total bilirubin) resolve, stabilize, or return to within the normal range or to baseline levels.
- Consultation with a specialist such as a hepatologist should be considered.

- Liver imaging (ie, ultrasound, magnetic resonance imaging, CT scan) should be considered.
- For Criterion b, the case must be reported as an SAE if the criterion is met after initiation of study drug administration.

3. Follow-up Examination

When any of the abnormal liver chemistry criteria are met, the following assessments should be performed at the follow-up visit(s) and reported by completing the appropriate eCRF page:

- Clinical symptoms course
- Alcohol use
- Risk factors for nonalcoholic steatohepatitis (NASH), such as diabetes, obesity, and hypertriglyceridemia
- Autoimmune hepatitis/cholangitis
- Wilson's disease
- Laboratory assessments
 - Viral hepatitis serology
 - o Hepatitis A IgM antibody
 - Hepatitis B surface antigen (HBs antigen) and Hepatitis B core antibody (HBc antibody)
 - o Hepatitis C RNA
 - o Hepatitis E IgA antibody
 - o Cytomegalovirus IgM antibody
 - o Epstein-Barr viral capsid antigen IgM antibody
 - For patients with total bilirubin $>1.5 \times ULN$, conjugated bilirubin
 - Complete blood count with differential to assess for eosinophilia

4. Drug Discontinuation Criteria Due to Abnormal Liver Chemistry Tests

[figure not shown]
Study drug must be discontinued if any one of the following criteria is met:

- AST or ALT >8 × ULN, confirmed by follow-up testing (ie, initial abnormality is confirmed on subsequent testing), regardless of medical history or physical examination findings
- AST or ALT >5 × ULN, with elevations for more than 2 weeks or development of concomitant signs or symptoms consistent with hepatitis or hypersensitivity (eg, fatigue, nausea, vomiting, right upper quadrant pain or tenderness, jaundice, fever, rash, or eosinophilia of >5%)
- AST or ALT >3 × ULN and total bilirubin >2 × ULN or, if measured, PT or INR >1.5, confirmed by follow-up testing (ie, initial abnormality is confirmed on subsequent testing), regardless of medical history or physical examination

findings. (Note: The specified INR threshold does not apply to patients receiving anticoagulant therapy.)

- AST or ALT >3 × ULN, with signs or symptoms consistent with hepatitis or hypersensitivity (eg, fatigue, nausea, vomiting, right upper quadrant pain or tenderness, jaundice, fever, rash, or eosinophilia of >5%), confirmed by follow-up testing (ie, initial laboratory abnormality is confirmed upon subsequent testing)
- AST or ALT >5 × ULN and \leq 8 × ULN and the patient cannot be followed up weekly

Appendix Figure 2-1 Management and Discontinuation Criteria for Abnormal Liver Chemistry Tests: Algorithm

- Following the initial observed elevation, every effort should be made to have the patient return to the clinic within 72 hours to repeat liver chemistry tests and for further hepatic evaluation.
- Patients must be monitored 2 to 3 times per week until liver chemistry tests (ALT, AST, ALP, total bilirubin) resolve, stabilize, or return to within the normal range or to baseline levels.
- Consultation with a specialist such as a hepatologist should be considered.
- Liver imaging (ie, ultrasound, magnetic resonance imaging, computed tomography) should be considered.
- * The specified INR threshold does not apply to patients receiving anticoagulant therapy.
- [≠] If the EDC system is unavailable or technical difficulties are encountered, report by completing the paper Liver Event Form and sending by fax or e mail to the sponsor. Local fax numbers and the e-mail address are provided in Section 7.6.5.7.2.

Confidential Page 108 of 110

S-600918 Shionogi Clinical Study Protocol: 1812VA323 Version 3 10 Sep 2020

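### When no repeat liver test is obtained, the mandatory stopping list in Appendix 2 is not ordered by severity: it can bind at >5 to ≤8 × ULN but not for an asymptomatic patient above 8 × ULN, nor at >3 to 5 × ULN with the bilirubin/INR finding or symptoms

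*Protocol*

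**What the plan says.** Protocol Section 4.5.2 makes discontinuation compulsory for a patient who meets the liver criteria in Appendix 2. Section 4 of that appendix opens with "Study drug must be discontinued if any one of the following criteria is met" and gives five criteria:

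1. "AST or ALT >8 × ULN, confirmed by follow-up testing".
2. AST or ALT above 5 × ULN, "with elevations for more than 2 weeks or development of concomitant signs or symptoms consistent with hepatitis or hypersensitivity". It has no upper limit and no confirmation requirement.
3. AST or ALT above 3 × ULN with total bilirubin above 2 × ULN "or, if measured, PT or INR >1.5, confirmed by follow-up testing". This is called the bilirubin/INR finding below.
4. AST or ALT above 3 × ULN with signs or symptoms, again subject to confirmation on a later test.
5. AST or ALT above 5 and up to 8 × ULN "and the patient cannot be followed up weekly". No confirmation is required.

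Appendix 2, Section 2 asks sites to try to repeat the tests within 72 hours, gives no rule for a patient who does not return, and lets the investigator stop drug on clinical judgement. On later monitoring, Section 2 says "Every effort should be made to have the patients monitored 2 to 3 times per week", whereas the notes to Appendix Figure 2-1 say "Patients must be monitored 2 to 3 times per week until liver chemistry tests".

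**The concern.** A mandatory stopping list is there to fix what does not depend on discretion, and one would expect it to bind at least as firmly for larger or more complex abnormalities as for smaller ones. Here, failure of follow-up triggers a stop only in the middle band. Above that band, and in the bilirubin/INR and symptom criteria below it, the same failure removes the confirmation on which the criterion depends.

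The setting is realistic. Version 3 was written for patients who may be unable to return to site, and under Section 7.2 a patient not expected back can receive the remaining 3 weeks of drug at Visit 4. Visit 4 is also the first on-treatment liver sample, and Section 7.6.2.1 schedules none at Visit 5.

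There is a further tension. Section 7.6.5.7.1 and Appendix 2, Section 2 treat the bilirubin/INR finding as a serious adverse event and do not ask for confirmation. One unconfirmed result can therefore be a reportable serious event and yet trigger no mandatory stop.

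**Working it through.** The plan gives no figure to reproduce; the check is one of rule logic.

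**Set-up.** The five Section 4 criteria were applied to every combination of AST/ALT band (>3 to 5, >5 to 8, above 8 × ULN; tested at 4, 6 and 10), bilirubin/INR finding (no or yes) and signs or symptoms (no or yes): 3 × 2 × 2 = 12 profiles. Two situations were compared:

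- A: no repeat test is obtained, elevation beyond 2 weeks cannot be shown, and weekly follow-up is not possible.
- B: a retest confirms the result, weekly follow-up is possible, and elevation beyond 2 weeks has not been shown.

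| AST/ALT | Bilirubin/INR | Symptoms | A: criteria met | B: criteria met |
|---|---|---|---|---|
| >3 to 5 | no | no | none | none |
| >3 to 5 | no | yes | **none** | 4 |
| >3 to 5 | yes | no | **none** | 3 |
| >3 to 5 | yes | yes | **none** | 3, 4 |
| >5 to 8 | no | no | 5 | none |
| >5 to 8 | no | yes | 2, 5 | 2, 4 |
| >5 to 8 | yes | no | 5 | 3 |
| >5 to 8 | yes | yes | 2, 5 | 2, 3, 4 |
| >8 | no | no | **none** | 1 |
| >8 | no | yes | 2 | 1, 2, 4 |
| >8 | yes | no | **none** | 1, 3 |
| >8 | yes | yes | 2 | 1, 2, 3, 4 |

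**Reading.** Ten of the 12 profiles are mandatory stops in B. Five of those ten (bold) meet nothing in A. All three abnormality criteria in Appendix 2, Section 1 are touched: a in its part above 8 × ULN without symptoms; b at >3 to 5 × ULN, and above 8 × ULN without symptoms; c at >3 to 5 × ULN.

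**Time at stake.** Visit 4 is Day 8 ± 2, so Day 6 to 10. Dosing left to Day 28 is 28 − 10 = 18 to 28 − 6 = 22 days. This is an upper range: it counts from sampling, not from the central laboratory's report, and applies to an abnormality first found at Visit 4. The next scheduled liver sample is Visit 6 (Day 27, window −2, so Day 25 to 27), which is 28 − 27 = 1 to 28 − 25 = 3 days before Day 28.

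**The 18-day stop.** Section 4.5.2 requires a stop when safety assessments cannot be done for more than 18 days between visits. Counted from Visit 4 on Day 6, 8 or 10, day 19 of the gap is Day 25, 27 or 29. Visit 5 safety assessments are vital signs and adverse events, so a kept Visit 5 restarts this clock without a liver test.

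**The case against.** The best case on the other side is that the protocol protects these patients in more ways than the Section 4 list suggests. Much of it stands.

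- A reader might infer that every patient above 8 × ULN, or with the bilirubin/INR finding, escapes the list without a retest. The text does not support that. The symptom limb of criterion 2 covers any symptomatic patient above 5 × ULN with no retest, and criterion 5 covers the bilirubin/INR finding at >5 to 8 × ULN when weekly follow-up is impossible.
- Being unable to attend weekly is not the same as having no repeat test. A patient above 8 × ULN who manages one repeat that confirms the value must stop. The protocol does not link the two conditions, and the gap needs the stronger one.
- A reader might infer that only investigator judgement remains. That is also too strong. There is the 18-day stop. Visiting nurses may take samples (Sections 7.6.2.3 and 8). The sponsor must be told within 72 hours, or within 24 hours for a serious adverse event.
- A reader might count three conflicting follow-up frequencies. There is one conflict: best effort against obligation for monitoring 2 to 3 times a week. Weekly, in criterion 5, is a stopping trigger and is compatible with either.
- The Figure 2-1 algorithm is not shown in the text reviewed and may deal with an unconfirmed result.

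These points narrow the gap but do not close it. The 18-day stop falls at or near the end of dosing. Nurse visits depend on local availability and approval. Reporting informs the sponsor but does not oblige a stop, and clinical judgement is permissive.

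**Conclusion.** The point holds in a limited form. With no repeat liver test, Section 4 is not ordered by severity. An asymptomatic patient at >5 to ≤8 × ULN who cannot be followed weekly must stop. No mandatory Section 4 criterion is met by (i) an asymptomatic patient above 8 × ULN, with or without the bilirubin/INR finding, or (ii) a patient at >3 to 5 × ULN with the bilirubin/INR finding or with symptoms.

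The size is 5 of the 10 profiles that would be mandatory stops once confirmed, with at most 18 to 22 dosing days remaining after a Visit 4 sample. These are counts of rule combinations, not of patients; the public text gives no frequency of liver events from which to estimate how many would be affected. The conclusion assumes that no retest is obtained, that weekly follow-up is impossible in the same patient, and that Figure 2-1 does not already settle the matter. It is a safety-rule inconsistency that should be corrected. It does not bear on the primary analysis, and it does not imply that either the confirmation requirement or the weekly criterion is the wrong one.

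**What to change.** The sponsor should reconcile the confirmation requirement in the first, third and fourth Section 4 criteria with the weekly follow-up criterion, so that each of the three Section 1 criteria has an applicable rule when a repeat test is not obtained. The text should also say how being unable to attend weekly relates to having no confirmatory test, and how a single unconfirmed bilirubin/INR result, already reportable as a serious adverse event, stands in relation to stopping. Section 2 and the notes to Figure 2-1 should state the 2 to 3 times weekly monitoring with the same force, and the figure should be checked against the agreed text.

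Which rule applies is for the sponsor's hepatic safety experts; none is proposed here. The cost is wording in one appendix and its figure, with no change to the planned analyses.

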FVC	forced vital capacity
ICIQ-SF	International Consultation on Incontinence Modular Questionnaire-Short Form
ie	that is
IRT	Interactive Response Technology
LCQ	Leicester Cough Questionnaire
MCS	mental components summary
MedDRA	Medical Dictionary for Regulatory Activities
PCS	physical components summary
PGIC	Patient Global Impression of Change
PK	pharmacokinetic(s)
PPS	per protocol set
PRO	patient reported outcome
PT	preferred term
PT-INR	prothrombin time international normalized ratio
S-600918	a selective P2X ₃ receptor antagonist
SAE	serious adverse event
SAP	statistical analysis plan
SD	standard deviation
SF-36	Short Form (36) Health Survey
SI	International System of Units
SMQ	Standardized MedDRA Query
SOC	system organ class
TEAE	treatment-emergent adverse events
US	United States Customary Units
VAS	Visual Analog Scale
WHO	World Health Organization
v III N	times the upper limit of the normal reference range

1. Introduction

This is a Phase 2b study of S-600918 for the treatment of refractory chronic cough. Coughing is a defense mechanism that eliminates sputum and foreign bodies from the airways. Chronic cough is defined as cough that persists for \geq 8 weeks. Refractory chronic cough is further defined as a chronic cough after the patient is treated for an underlying medical condition, as well as chronic cough for which an underlying medical condition has not been identified despite appropriate patient evaluation. An estimated 2% to 5% of the population of Europe, the United States, and Japan suffers from refractory chronic cough.

S-600918 is a P2X₃ receptor antagonist developed by Shionogi & Co., Ltd that is formulated for once daily oral administration. In previous studies, this class of drugs has shown an effect in suppressing the cough reflex among patients with refractory chronic cough. Four previous studies of S-600918 have been completed, including a phase 1 single ascending dose & food effect study, a phase 1 multiple ascending dose study, a Phase 1 drug-drug interaction study, and a phase 2 crossover study in refractory chronic cough patients. The data from these studies has informed the design of Study 1812VA323 (this VA323 study) and are discussed in further detail in section 1.2.2 of the protocol.

2. Objectives

The Primary Objective of this study is to determine the optimal dose of S-600918 in patients with refractory chronic cough by evaluating the change from baseline in 24-hour cough frequency (coughs per hour) with S-600918 compared with placebo.

The secondary objectives are:

- To compare the efficacy of S-600918 to that of placebo in patients with refractory chronic cough based on the following measurements:
 - Number of coughs per hour while awake
 - Number of coughs per hour while asleep
 - Severity of cough as assessed by the patient on the Visual Analog Scale (VAS)
 - Leicester Cough Questionnaire (LCQ)
 - o International Consultation on Incontinence Modular Questionnaire-Short Form (ICIQ-SF)
 - Short Form (36) Health Survey (SF-36), version 2
 - Patient Global Impression of Change (PGIC)
- To evaluate the safety of S-600918 in patients with refractory chronic cough.
- To assess the pharmacokinetics (PK) of S-600918 and its metabolite (S-600918 acyl glucuronide) in patients with refractory chronic cough.

3. Investigational Plan

3.1. Overall Study Design and Plan

This VA323 study is a phase 2b, multicenter, randomized, double-blind, placebo-controlled, parallelgroup, dose-selection study of 3 doses of S-600918 in patients with refractory chronic cough. A total of 372 patients are planned to be randomized in a 1:1:1:1 manner to either placebo, S-600918 50mg, S-600918 150mg, or S-600918 300mg, stratified by region (United States, Europe, Japan) and by hourly cough count based on the 24-hour cough count recording at Visit 1 (≥30 coughs/hour or <30 coughs/hour). The study duration for each patient is 8-10 weeks, with 18-28 days in screening (Visit 1 and 2), 28 days of treatment (Visit 3, 4, 5, and 6), and 14 days of follow-up (Visit 7) planned. Planned efficacy assessments will be cough counts, as measured by a VitaloJAK cough monitor, and several patient report outcomes & questionnaire responses, including weekly cough severity (VAS), LCQ, ICIQ-SF, SF-36, and PGIC. Further clinical assessments include, but are not limited to laboratory samples, vital signs, electrocardiogram (ECG), physical examinations, adverse events, concomitant medications, and pharmacokinetic samples. A detailed description of study assessments by visit can be found in

section 8 of the protocol, with a tabular summary given in Appendix 1 of the protocol which is also available within this SAP as Appendix 1.

Figure 3-1

° At Visit 3 (1 day after Visit 2)

3.2. Study Endpoints

3.2.1. Primary Efficacy Endpoint

The primary efficacy endpoint is the ratio of the average number of coughs per hour in 24 hours (based on cough counts recorded by the VitaloJAK cough monitor) after administration of study drug for 4 weeks to that at baseline. For cough count data, baseline is defined as the last non-missing observation prior to the initiation of study treatment. As such, a ratio value that is below 1 will represent a reduction in cough, while a value above 1 will represent an increase in cough.

The VitaloJAK cough monitor has European Conformity (CE) marking in the European Union and 510(k) approval from the United States Food and Drug Administration (FDA). It is widely used in global studies and consists of a microphone and a recording device and was designed to acquire, record, and store ambulatory cough sounds for up to 24 hours. The VitaloJAK cough monitor does not measure the intensity or the impact of cough.

In this study, the VitaloJAK cough monitor will be applied to patients at Visit 1 (Screening), Visit 2 (Day - 1), Visit 4 (Day 8), Visit 5 (Day 22), and Visit 6 (Day 27). On each of these visit days, patients will be instructed to wear the monitor continuously for 24 hours. Patients will then remove the monitor and return it to the site. The site will upload the data from the cough monitor to Vitalograph, the cough monitor analysis institution. The data will be analyzed by cough analysis technicians and provided for further statistical analysis. The cough data provided for statistical analysis will contain a chronological log of coughs, sleep, wake, and recording times while each of awake and asleep. From this, the average

coughs per hour in the 24 hours following the activation of the cough monitor will be calculated based on the recording time.

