3.4. Dose Adjustment/Modifications

No dose adjustments or modifications are allowed in this study.

4. General Statistical Considerations

Unless otherwise noted, continuous variables will be summarized based on the number of non-missing observations (N), arithmetic mean (Mean), standard deviation (SD), median, minimum, and maximum values. Categorical variables will be summarized based on the frequency count and the percentage of patients in each category. All statistical tests will be performed at the 0.05 significance level using 2-sided tests, unless otherwise noted, and statistical testing will not be adjusted for multiple comparisons.

Study data will be presented in by-patient data listings. In general, all tables will be presented by treatment group. Individual patient data, PK data, and any derived data will be presented by treatment group (study drug) (S-600918 50 mg, S-600918 150 mg, S-600918 300 mg, and placebo). All analyses and tabulations will be performed by using SAS Version 9.2 or higher and WinNonlin Version 6.3 or higher.

Baseline will be defined as the last valid assessment recorded prior to the first administration of study drug unless otherwise specified.

For summaries, patients will be counted only once within each planned visit. In these summaries, the visit windows will follow the windows given in the protocol, which are repeated in Appendix 1 of this SAP. However, +1 day will be allowed at the end of the Visit 6 time window for analysis.

Visit	Target Day	Window Start Day	Window End Day
Visit 1 / Screening	-18	-28	-18
Visit 2 / Day -1	-1	-1	-1
Visit 3 / Day 1	1	1	1
Visit 4 / Day 8	8	6	10
Visit 5 / Week 3	22	20	24
Visit 6 / Week 4	27	25	28

Table 4-1: General Analysis Visit Wind

In the event that more than one observation is recorded within one of these windows, then, among these records within the window, the record occurring at the planned visit in the CRF will be used. If no records occurred at the planned visit within the window, then records occurring at any unplanned visits within the visit window will be considered, and the record occurring closest in time to the target visit day will be used. Results that are recorded at an Early Discontinuation visit may be summarized at a planned visit if the Early Discontinuation visit falls within the window for the planned visit, and the planned visit has not occurred.

Study days will be calculated using the date of the first administration of study drug as follows:

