4.1. Sample Size

The sample size has been determined using the results of the VA322 proof-of-concept study. In that VA322 study, the mean (\pm SD) of the common log-transformed ratio of cough frequencies per hour in 24 hours after 2 weeks of treatment to that at baseline was -0.327 (0.379) in the S-600918 150-mg treatment (N = 31) and -0.160 (0.363) in the placebo treatment (N = 30). The difference in the common log-transformed ratio of the cough frequencies per hour in 24 hours after 4 weeks of treatment to that at baseline between each S-600918 dose group and placebo and the standard deviation (SD) in each treatment group in the Phase 2b study were assumed to be the same as those after 2 weeks of treatment observed in the proof-of-concept study, and -0.163 and 0.371, respectively. As a result, the effect size, ie, the difference divided by the SD, was determined to be -0.44. Based on this assumption, the sample size required to assure 80% power with a 2-sided 5% level of significance was calculated to be 83 patients per treatment group. Allowing for exclusion of 10% of patients per treatment group, 93 patients per treatment group will be needed. Therefore, the planned sample size at randomization was determined to be a total of 372 patients.

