6.2. Baseline Disease Characteristics

Average cough counts per hour in 24 hours at Visit 1 and Visit 2 and baseline will be summarized using descriptive statistics by treatment group. In addition, the weekly severity of cough (VAS) at baseline, the LCQ at baseline, and baseline pulmonary function test results, including FVC (L), FEV1 (L), and FEV1/FVC ratio will be summarized using descriptive statistics. As well, the duration of chronic cough (months; ((date of screening – reported start date of chronic cough) + 1) / 30.4375) will be summarized using descriptive statistics by treatment group. When part of the start date or end date is missing, 15^{th} of the month for missing day and July 1^{st} when month and day are missing will be used.

Cough-related history will be recorded on the eCRF and coded using MedDRA v22.1. The number and percentage of patients with any cough-related history will be summarized by treatment and overall for each preferred term. Cough-related history will also be listed with the calculated duration of each history. For the calculation of duration, partial dates will be handled as above, using the 15th of the month for missing day and July 1st when month and day are missing. Ongoing histories will use the date of enrollment as the end date for calculating duration.

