8.1.1. Primary Analysis

The null hypotheses of equality between the treatment and placebo effects will be tested using a mixed model, containing treatment group, week (as a classification term), and the interaction between treatment group and week as fixed effects; patient as random effect; and region and the common logarithm of the frequency of coughs per hour at baseline as covariates. In this model, the covariance structure will be given as unstructured, and the degrees of freedom will be derived using the Kenward-Roger method. Should the model fail to converge using the unstructured covariance, compound symmetry will be used. Using this model, the log-transformed ratio of the number of coughs per hour in 24 hours after 4 weeks of administration of study drug will be used to evaluate the null hypothesis at each dose level of S-600918 at the 2-sided alpha level of 0.05 among the FAS.

The primary analysis will summarize each of these three 2-way comparisons, presenting the estimate for the difference of the effects of treatment at Visit 6, the 95% confidence interval for this difference, and the p-value based on the hypothesis and model described above. Furthermore, the time course of the treatment effect for each treatment group will be plotted with the mean and 95% confidence interval.

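### The primary model adjusts for one pre-dose 24-hour cough count and leaves out the continuous Visit 1 count, which may cost some precision

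*SAP*

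**What the plan says.** The monitor is worn for 24 hours at Visit 1 and again at Visit 2, both before dosing (SAP 3.2.1). The SAP then uses one of the two: "For cough count data, baseline is defined as the last non-missing observation prior to the initiation of study treatment". SAP 8.1 makes this Visit 2. Visit 1 stands in alone if the Visit 2 count is missing or its recording ends after the first dose.

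The primary model (SAP 8.1.1) adjusts for "region and the common logarithm of the frequency of coughs per hour at baseline as covariates". Protocol 9.10.3.1 lists the same covariates, and so does the ANCOVA in SAP 8.1.2.

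The Visit 1 count has other uses. Inclusion criterion 6 requires at least 10 coughs per hour at Visit 1, and randomisation is stratified on that count at 30 per hour. It defines a subgroup (SAP 8.1.4) and is described at baseline: "Average cough counts per hour in 24 hours at Visit 1 and Visit 2 and baseline will be summarized" (SAP 6.2). Neither its continuous value nor the stratum is in the primary model, and no sensitivity analysis uses both recordings.

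**The concern.** One 24-hour count measures a patient's usual cough rate with error. SAP Appendix 2 sets no minimum recording length for the rate; only recordings under 1 hour are rejected. A short Visit 2 recording could therefore be a patient's whole baseline. If Visit 1 tells us something about the Week 4 count beyond what Visit 2 tells us, leaving it out keeps explainable between-patient variance in the residual and widens the interval for every dose against placebo. Dose selection rests on those three comparisons. The information is already collected, and because it precedes randomisation it can be used as a covariate without introducing bias.

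**Working it through.** **1. The plan's own figure.** Inputs (SAP section 4 and 4.1): two-sided 5%, 80% power, difference and SD of −"0.163 and 0.371, respectively". The standardised effect is 0.163 / 0.371 = 0.44. A two-sample noncentral-t calculation gives 79.9% power at 82 per group and 80.3% at 83, so 83 reproduces. Then 83 / 0.9 = 92.2, rounded up to 93, and 4 × 93 = 372.

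**2. What 0.371 measures.** The proof-of-concept SDs of the log10 ratio are 0.379 and 0.363. Pooled, √((0.379² + 0.363²)/2) = 0.371. It is the SD of the log ratio itself, before any baseline covariate.

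**3. Formulas.** Let *s* be the SD of a log10 count and ρ the correlation of Visit 2 with Visit 1 and with Visit 6. From 2s²(1 − ρ) = 0.371² = 0.1376, ρ = 1 − 0.1376/(2s²). The documents give neither quantity, so I assume *s* = 0.35, 0.45 and 0.55, which gives ρ = 0.44, 0.66 and 0.77.

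- Residual variance with Visit 2 alone: 0.1376 × (1 + ρ)/2. Because log baseline is a covariate, modelling the ratio or the Week 4 count leaves the same residual.
- Proportional cut from adding Visit 1 separately: ((r − ρ²)/(1 − ρ²))², where *r* is the correlation of Visit 1 with Visit 6.
- Equal correlation (r = ρ): cut = (ρ/(1 + ρ))², or 9%, 16% and 19%.
- *r* halfway between ρ and ρ²: one quarter of that.
- Full first-order decay (r = ρ²): zero.

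**4. With the entry rule.** Requiring at least 10 per hour at Visit 1 narrows that covariate and reduces the gain. I simulated this with assumed medians of 20, 30 and 40 per hour (600,000 draws per scenario before selection). Power is at 83 per group for a difference of 0.163, using the residual SD in the two-sample formula; region and the repeated visits are ignored.

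| s | ρ | Pattern | Variance cut | Power, Visit 2 only | Power, both |
|---|---|---|---|---|---|
| 0.35 | 0.44 | equal | 6–8% | 92% | 94% |
| 0.45 | 0.66 | equal | 11–14% | 88–89% | 92% |
| 0.55 | 0.77 | equal | 14–16% | 86–87% | 91% |
| 0.35 | 0.44 | halfway | 1.5–2% | 91–92% | 92% |
| 0.45 | 0.66 | halfway | about 3% | 87–88% | 88–89% |
| 0.55 | 0.77 | halfway | 3.5–4% | 85% | 87% |
| all | all | full decay | 0% | 85–91% | unchanged |

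The power gain is about 1.5 to 5 points with equal correlation, 0.3 to 1.4 halfway, and none with full decay. If the two-level Visit 1 stratum were already in the model, the continuous count would still remove 2% to 11% under equal correlation.

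**5. Separate covariates or an average.** Take both correlations with Visit 2 as 0.8, so Visit 2 alone leaves 1 − 0.64 = 0.36 of the variance. The mean of the two recordings leaves 1 − (r + 0.8)²/3.6.

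- r = 0.8: both approaches cut the variance by 20%.
- r = 0.7: the mean leaves 0.375, which is 4% worse than Visit 2 alone; separate covariates are 3% better.
- r = 0.64: the mean leaves 0.424, which is 18% worse; separate covariates are neutral.

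**The case against.** The strongest reply is that nothing here is wrong. The last pre-dose value is a conventional baseline, it is already a continuous covariate, and on the SAP's inputs the model is adequately powered. The gain may be nil. Visit 1 is 17 to 27 days before Visit 2 and, with Visit 6 on Day 27 and no Day 0, 44 to 54 days before Visit 6. It is the selection visit, and exclusion criterion 26 lets some therapies stop only at Visit 1, so its count may precede full washout. Each of these could weaken its link with Week 4. Changing the model also departs from the protocol's covariate list.

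Most of this stands: the size is unknown, and the change is a gain in efficiency that must be declared. It does not defeat the proposal. The risk of doing worse belongs to averaging the recordings. With two separate covariates, an uninformative Visit 1 count gets a coefficient near zero and costs about one degree of freedom.

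A reader might also infer that every randomised patient has two usable pre-dose counts. Exclusion criterion 2 does require both recordings, but only on the site's initial assessment. SAP 8.1 and Appendix 2 provide for a Visit 2 count that is missing, centrally rejected or overlapping the first dose.

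**Conclusion.** The point holds as a possible loss of precision. The plan collects a second pre-dose count, relies on it for entry and stratification, and omits its continuous value from the primary model and the ANCOVA. The likely benefit of using it is a residual variance cut between 0% and about 16%, and 0 to about 5 points of power from a starting level of about 85% to 92%. These ranges rest on the assumed count SDs (0.35 to 0.55), medians (20 to 40 per hour) and correlation patterns.

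Two stronger readings are not supported. One is that the single baseline biases the comparisons. Baseline is measured before randomisation and defined identically in all groups, so it does not. The other is that power would rise from 80% to about 85%. That uses 0.371 as the residual SD after baseline adjustment, whereas SAP 4.1 gives it as the SD of the log ratio. The two can coincide only if adjusting for baseline removes no variance.

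**What to change.** Before unblinding, in SAP 8.1.1 and 8.1.2:

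- Add log10 coughs per hour in 24 hours at Visit 1 as a second continuous covariate beside log10 baseline. Do not average the two recordings.
- Keep the denominator of the ratio as defined.
- Where baseline falls back to Visit 1, enter the Visit 1 value for both covariates.
- Record the change from protocol 9.10.3.1 in SAP section 13, which now reports no changes.

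The cost is one degree of freedom, a short SAP edit and a declared departure from the protocol's covariate list. No new data are needed.
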